### III. Inclusion/exclusion criteria.

- a. Inclusion criteria: obtaining prenatal care at UIC; initial prenatal hemoglobin between 10.0 – 11.9 g/dl; 18 - 45 years of age; spontaneous/natural conception; singleton pregnancy; < 20 weeks gestation; and willing to: a) fast for at least 2 hours prior to research data collection visits (3 occasions), b) agree to randomization; c) ingest Lp299v + standard PNVI or standard PNVI + placebo daily through delivery; c) refrain from **ALL** other supplements including other PNVs unless medically indicated (e.g., folate); d) attend 3 research data collection visits at UIC; e) undergo 3 venipunctures; and f) come to UIC on 4-5 occasions (separate from research visit but will be coordinated around standard clinical care visits) to pick up supplements and have study compliance monitored/checked. Women will also be able to read and write English, and have access to a smart phone. Also, women must agree to refrain from **ALL** other pre and probiotic supplements (unless medically indicated) including Activia yogurt, Kefir, Tropicana Probiotic, and Good Belly products while in the study.
- b. Exclusion criteria: Autoimmune disorder; current or previous premature rupture of membranes or clinical chorioamnionitis; current bacterial or viral infection; oral antibiotic use in the last 3 months; receiving steroid or anti-inflammatory treatment; previous bariatric surgery; malabsorptive condition; current hyperemesis; hematologic disorder (i.e., sickle cell disease or hemochromatosis); current tobacco use or within the past 1 month; current alcohol consumption; current drug use; or type 1 or 2 diabetes given these factors may influence the biological markers.

**IV. Randomization.** Women will be randomized to the Lp229V + standard PNVI or standard PNVI + placebo following the baseline visit.

**V. Treatment groups.** Women will be assigned to one of two treatment groups as described below.

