***b. Research follow-up visits (24–28 and 34–36 weeks gestation)***

Reminder Phone Call, Text, and Email: Women will be called or texted and emailed 2-3 days before the visit. Women will be reminded of their appointment time and location, asked to not eat for at least 2 hours before the appointment, and reminded about the visit procedures.

Data collection procedures: Women will be weighed with an electronic scale; a venous blood sample (30 ml) obtained by research staff; 2 rectal swab samples collected, optional; and surveys (described in detail below) will be interviewer administered by trained staff. If there is extra blood available from the venous blood sample and the patient consents, it may be used for future research to learn more about how to prevent, detect, or treat other health problems in pregnancy.

Surveys: Women will be asked to complete the following surveys:

1. 24 hour diet recall. The 24-hour diet recall will be collected using Nutrition Data System for Research (NDSR) software, a computer-based software application developed at the University of Minnesota that facilitates the collection of dietary recalls in a standardized fashion. Dietary intake data gathered by interview is governed by a multiple-pass interview approach. Dietary supplement use will be assessed in conjunction with collection of 24-hour dietary recalls using

the Dietary Supplement Assessment Module included in NDSR. Use of all types of dietary supplements and non-prescription antacids are queried in the module. The RAs are NDSR certified through the University of Illinois Cancer Center Diet and Behavior Shared Resource.

2. GI symptoms checklist. This short survey probes for recent GI problems including abdominal pain, nausea, constipation, and diarrhea.
3. Mood and Anxiety Symptom Questionnaire – Anhedonia subscale (MASQ-AD). This is a 22-item subscale of the MASQ, is a measure of depressive disorders.
4. Patient Health Questionnaire (PHQ-9). This is a 9-item questionnaire assessing depressive symptoms.
5. Edinburgh Postnatal Depression Scale (EPDS). This is a 10-item scale intended to measure depressive symptoms during the perinatal period.
6. Perceived stress scale. This is a 10-item scale intended to measure perceived stress over the last month.

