**e. Labor and delivery.**

Reminders for contacting research staff and participant tracking. During the 34–36 gestational week research visit and/or at the final pill pick, women will be provided a laminated card with the study number and staff personal contact information. Women will be instructed to contact the research team when they are admitted to UIC labor and delivery. In addition, we will follow the progress of these women closely via phone call, text message, email and through the patient EHR until they are admitted to UIC labor and delivery. UIC labor and delivery staff will also be in-serviced regarding the study procedures.

- 1) Maternal venous blood draw: Following admission, as part of routine care, women will undergo a venous blood collection by labor and delivery staff. As part of this routine care, we will request an additional two tubes of blood (30 ml) for research purposes. If there is extra blood available from the venous blood sample and the patient consents, it may be used for future research to learn more about how to prevent, detect, or treat other health problems in pregnancy.
- 2) Umbilical venous cord blood collection (placental cord blood): Immediately following delivery, the research team will collect a maximum of three tubes of umbilical venous cord blood (~30 mL). If a research participant chooses to bank their umbilical cord blood, and therefore the research team cannot obtain 30 mL of umbilical cord blood, the research team will draw 30 mL of placental blood for analysis. If there is extra cord blood available from the cord blood sample and the patient consents, it may be used for future research to learn more about how to prevent, detect, or treat other health problems in pregnancy.
- 3) Placenta (20 grams): After the cord blood has been obtained, the placenta will be placed in a basin with lid and transferred to the [name] lab space in COMRB. Following placental

characteristics will be examined (i.e., weight, length) and processed for analysis and stored at -80C until later analysis.

- 4) Maternal and infant labor and delivery data: Following participant discharge, a research team member will abstract pertinent maternal and infant L&D data (i.e., route of delivery, infant weight, and infant length) from the EHR.

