#### **CHANGES DUE TO COVID-19 PANDEMIC, 3.17.2020:**

To allow for the provision of mailed supplements during the coronavirus-19 pandemic and alterations to our in person data collection methods. This is an effort to reduce subject and researcher contact while maintaining study integrity for those already enrolled.

1) Supplement refills: Supplement refills will be mailed. Subjects are being informed by phone regarding the change in procedure. UIC Investigational Drug Service will continue to dispense the supplements. UIC IDS will provide a labeled study bottle that fits with the Smart Caps being used to monitor adherence (already at home with the participant) and generic capped study bottles containing the newly dispensed supplements (probiotic/placebo or supplement). The supplements will be mailed using an overnight courier (e.g., UPS). When the pills are received, study staff will instruct over the phone/FaceTime how to refill their supplement bottles as

well as conduct a hand pill count. Subjects will be asked to save their remaining pills in the generic pill bottles provided and to return to the research staff at a later date.

2) Surveys. All surveys will be conducted by phone or via a RECap link (subject preference) that coincide with study and pill refill visits.

3) Blood draws. Subjects will be sent labeled blood tubes to have their blood drawn at their 24-28 week and third trimester clinically indicated blood draw at UIC Clinical Phlebotomy. Subjects will then bring their blood samples to a locked specimen box located outside of the UIC CRC. The subject will alert the study staff and blood tubes will be picked up by the PI processed and stored or sent to Quest Diagnostics.

4) Anthropometrics. Gestational weight at a date the coincides with our defined study visits (24-28 weeks, & 34-36 weeks) will be obtained from the EHR vs. physically measured.

5) Labor and delivery samples. Nurse mid-wives ([name] and [name]) working clinically at the time of admittance for delivery, will assist with obtaining maternal blood and venous cord blood. The PI will be alerted by phone call or text message and will retrieve the samples for processing.

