The rectal swabs microbial 16s rRNA sequencing data will be analyzed with QIIME and PICRUSt. Baseline microbial abundance, diversity, and predicted microbial metabolisms will be assessed. For feasibility, # of charts screened, prescreening eligible, approached, and enrolled will be calculated. The # of visits completed at each time point and end of study attrition will be determined and differences between groups calculated. Adherence (# of pills consumed) and # of SAEs/AEs will be calculated and compared between groups. Maternal stress response, maternal iron-related parameters, and inflammation at baseline, 24-28 weeks, 34-36 weeks and labor and delivery, will be evaluated using repeated measures ANOVA and ANCOVA to adjust for baseline differences. Infant iron status at delivery will be compared between groups (Student's t-test). Microbial abundance, diversity and microbial metabolisms will be compared between groups at baseline, 24-28 weeks, 34-36 weeks (Student's t-test/Mann Whitney U) and within group changes at 24-28 weeks and 34-36 weeks will be determined. The mediating effects of maternal rectal swabs microbiome, systemic inflammation and iron regulatory responses on the relationship between Lp299v on maternal stress- and iron-related outcomes will be explored using generalized linear models. Multiple comparisons and false discovery rate adjustments will be used accordingly.

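### The delivery blood draw is taken under different conditions from the other three, but the planned repeated-measures ANOVA makes no allowance for a different variance at delivery

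*Combined protocol and SAP*

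**What the plan says.** **Scheduled draws.** The inclusion criteria (section III) ask women to "fast for at least 2 hours prior to research data collection visits (3 occasions". The reminders for the two follow-up visits (section VI.b) repeat this: women are "asked to not eat for at least 2 hours before the appointment, and reminded about the visit procedures". No clock time is fixed for these draws.

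**Delivery draw.** Section VI.e, item 1 uses a routine draw instead: "Following admission, as part of routine care, women will undergo a venous blood collection by labor and delivery staff". The research sample is added to it: "As part of this routine care, we will request an additional two tubes of blood (30 ml) for research purposes". Fasting, time of day, time since the last tablet and stage of labor are not mentioned. The delivery chart abstraction (item 4) gives route of delivery, infant weight and infant length as its examples.

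**COVID-19 changes.** The 24-28 week and later samples move to the 24-28 week and "third trimester clinically indicated blood draw at UIC Clinical Phlebotomy". The fast is not restated. The delivery sample is still taken around admission.

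**Analysis.** Section XIII states: "Maternal stress response, maternal iron-related parameters, and inflammation at baseline, 24-28 weeks, 34-36 weeks and labor and delivery, will be evaluated using repeated measures ANOVA", together with ANCOVA to adjust for baseline differences. It also describes a two-way general linear model by treatment and time. Single time-points are tested only if there is a significant effect over time, and only 24-28 and 34-36 weeks are named. Specific Aim 1 nevertheless hypothesizes better iron status at delivery as well.

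**The concern.** A classical repeated-measures ANOVA pools the within-woman error over occasions. Its treatment-by-time test is valid without correction only if the differences between occasions all have the same variance. The delivery sample is the occasion most likely to break this. Women may be in active labor, being induced or awaiting a planned cesarean, and the time since food or the daily iron-containing tablet is uncontrolled. The Background links stress to inflammation, inflammation to hepcidin, and hepcidin to iron handling. It is therefore plausible, though not shown in the documents, that serum iron, transferrin saturation, hepcidin, IL-6, hs-CRP and 17-hydroxycorticosterone vary more between women at delivery.

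Two things are at stake. The overall test could miss an effect that is present at the two scheduled follow-up visits, and because it gates the single-visit tests, those might then never be run. The overall test could also reject too often when there is no effect. No visit-specific variance, sphericity correction or analysis without delivery is planned.

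**Working it through.** The plan gives no power, SD or effect size for its 40 women, so there is no figure to reproduce. What follows is an illustration under stated assumptions.

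**Inputs from the documents**
- Total sample 40 (section I); two-sided level 0.05 (section XIII).
- Withdrawal limit 15% (section VI.c): 40 × 0.85 = 34. The allocation ratio is not stated; at 1:1 this is 17 per arm.

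**Assumed inputs**
- Scheduled-visit SD 1; correlation ρ between scheduled visits 0.3 to 0.7 (main case 0.5).
- Arm difference 0 at baseline and 0.8 SD at every later visit.
- Delivery SD r. The excess is independent noise, so the covariance with other visits stays at ρ.

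**1. Comparison averaged over post-baseline visits**
- Variance of the two-visit mean: (1 + ρ)/2. At ρ = 0.5 this is 0.75.
- Variance of the three-visit mean: (2 + r² + 6ρ)/9.
  - r = 1: (2 + 1 + 3)/9 = 0.667. Ratio 0.667/0.75 = 0.89, so including delivery helps. Power is 0.82, against 0.77 with two visits.
  - r = 2: (2 + 4 + 3)/9 = 1.00. Ratio 1.00/0.75 = 1.33, so variance rises by 33%. Power is 0.65, against 0.77.
- Setting the two variances equal gives the break-even: r² = 9(1 + ρ)/2 − 2 − 6ρ = 2.5 − 1.5ρ.
  - ρ = 0.3: r = √2.05 = 1.43
  - ρ = 0.5: r = √1.75 = 1.32
  - ρ = 0.7: r = √1.45 = 1.20
- Baseline adjustment subtracts ρ² from both variances, so the break-even does not move. The penalty beyond it is larger: at r = 2 and ρ = 0.5, 0.75/0.50 = 1.5.

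**2. Treatment-by-time test (simulation, ρ = 0.5, 17 per arm)**

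| Analysis | Power | False-positive rate |
|---|---|---|
| Common variance, uncorrected, delivery omitted | 0.65 | 0.05 |
| Common variance, uncorrected, delivery included, r = 2 | about 0.27 | about 0.08 |
| Unstructured covariance, delivery included, r = 2 | about 0.56 | 0.05 |

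Letting the correlation of delivery with the other visits range from 0.2 to 0.5, the uncorrected test has these properties:
- r = 1: power 0.53 to 0.65
- r = 1.5: power 0.38 to 0.51
- r = 2: power 0.25 to 0.34, false-positive rate 0.07 to 0.08
- r = 3: power 0.16 to 0.17, false-positive rate about 0.09

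If the variances are in fact equal, unstructured covariance costs about 0.04 in power.

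**The case against.** **The size of the problem is unknown.** No document gives an SD at any visit or says how these markers respond to labor; the Background argues from chronic stress. At equal SD the averaged comparison gains from delivery. Section XIII also plans to transform non-normal variables or use non-parametric tests, which may reduce unequal spread. All of this stands, and the figures above are conditional for that reason.

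**The common-variance test is not spelled out.** A general linear model for repeated measures can also be tested multivariately, which does not assume equal variances, or with a sphericity correction. The correction would restore the error rate but not the lost power. The plan names none of these, so the uncorrected test is one permitted reading and not a certainty.

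**The contrast in draw conditions is less clean than it looks.** A reader might infer that delivery blood is unfasted and the rest fasted. Section VI.e sets no rule, but it does not say that women will have eaten. The scheduled fast is only 2 hours, and the COVID-19 changes do not restate it. Labor itself remains the clearer difference.

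**Stronger readings that the documents do not support**
- *Bias.* A reader might infer that chance imbalance in labor status would produce a spurious late probiotic effect. Under randomization that is ordinary sampling error, which the test allows for if its variance model is right.
- *Lost precision at 24-28 and 34-36 weeks themselves.* If each is tested on its own data, delivery variance does not enter. The route to harm is the overall test that gates them.
- *A much larger sample penalty.* Holding the delivery correlation at 0.5 while doubling its SD gives (2 + 4 + 1 + 4)/9 = 1.22, and 1.22/0.75 = 1.63, or 63% more women. That doubles the covariance with the other visits, so it is not added noise. Independent noise gives 33%.
- *Delivery should leave the main analysis.* That would give up a time-point that Aim 1 names.

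**This is a pilot.** With 40 women and no power target, no planned power is being eroded. That lowers the priority, but the remedy is inexpensive.

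**Conclusion.** The point holds as a precision and error-rate weakness, conditional on greater spread at delivery. It is established that the delivery draw has no stated conditions and that it enters the same repeated-measures analysis as the planned visits with no provision for a different variance. It is assumed that the delivery SD is larger.

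At twice the scheduled SD, under the main-case assumptions, the uncorrected treatment-by-time test falls from power 0.65 without delivery to about 0.27 with it, with a false-positive rate of about 0.08. The averaged comparison is harmed only above about 1.2 to 1.4 times the scheduled SD; at twice the SD its unadjusted variance rises by 33%. Neither result implies bias between the arms. This is a worthwhile, low-cost improvement to the analysis plan and not a flaw that invalidates the trial.

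**What to change.** 1. For all maternal blood markers, replace the common-variance repeated-measures ANOVA with a baseline-adjusted mixed model with treatment, visit and their interaction, and an unstructured (visit-specific) covariance.
2. Report the arm contrast separately at 24-28 weeks, 34-36 weeks and delivery, without making it depend on an overall time effect. This keeps the Aim 1 claim at delivery. The false discovery rate adjustment already mentioned in section XIII should say how it covers these contrasts.
3. For serum iron, transferrin saturation, hepcidin, IL-6, hs-CRP and 17-hydroxycorticosterone, add a sensitivity analysis of 24-28 and 34-36 weeks without delivery.
4. With the delivery data already to be abstracted, record draw time, labor status and, where charted, last meal and last tablet. Use these for description only. Do not stratify the arm comparison on labor status, which arises after randomization and could be affected by treatment.

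**Cost.** Revised analysis wording, a few chart fields, a few more covariance parameters, and about 0.04 in power if the variances turn out equal. No new visit, sample or assay is needed.

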**Specific Aim 1:** To determine the impact of consuming daily Lp299v + standard PNVI vs. standard PNVI + placebo beginning between 15-20 weeks gestation through delivery on maternal iron status and metabolism. To fully characterize maternal iron metabolism and regulators of maternal iron metabolism we will measure several blood-based markers including hemoglobin, hematocrit, ferritin, transferrin receptor, transferrin saturation, serum iron, erythropoietin, systemic inflammation and hepcidin at baseline, 24-28 and 34 - 36 weeks gestation, and at

delivery. *Hypothesis: Women consuming Lp229v will have superior iron status at –24-28 and 34 - 36 weeks gestation and at delivery compared to control women.*

**Specific Aim 2:** To determine colonization and propagation of the gut microbial community with Lp299v from rectal swabs collected at baseline, 24-28 weeks and 34 - 36 weeks gestation in women consuming Lp299v + standard PNVI vs. standard PNVI + placebo. *Hypothesis: Women consuming LP299v will have greater colonization and propagation of Lp299v in their rectal swabs at –24-28 week and 34 - 36 weeks gestation compared to women consuming PNVI + placebo.*

**Specific Aim 3:** To explore the effect of daily oral Lp299v vs. placebo on infant iron status at delivery. Infant iron status will be measured (via cord blood at delivery) (i.e., hemoglobin, ferritin, transferrin, serum iron, and transferrin receptor). *Hypothesis: Infant of women consuming LP299v will have higher iron status at delivery.*

**Specific Aim 4:** To determine the feasibility and tolerability of daily oral Lp299v supplementation (15-20 weeks gestation-delivery). *Hypothesis: Feasibility and tolerability will be high in both treatment groups of the study for the duration of the trial.*

**Exploratory Aim 1:** There is some evidence that probiotic use can positively influence maternal health outcomes including mood. We will explore differences in the development of gestational hypertension, pre-eclampsia, and gestational diabetes using data extracted from the electronic health record (EHR). We will also examine changes to maternal stress response (i.e., serum 17-hydroxycorticosterone and hair cortisol via immunoassay) and self-reported stress, depression, anxiety, resilience, experiences of discrimination, childhood trauma, social support, post-traumatic stress, and spirituality via surveys in women consuming Lp299v + standard PNVI vs. standard PNVI + placebo.

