**a. Baseline (<20 weeks gestation).**

Reminder Phone Call or Text and Email: Women will be called or texted and emailed 2-3 days before the baseline visit. Women will be reminded of their appointment time and location, asked to not eat for at least 2 hours before the appointment, and reminded about the visit procedures.

Obtaining Informed Consent: Consent will be obtained using IRB approved materials by trained research staff at the baseline study visit before any study procedures take place.

Data collection procedures: Women will be weighed with an electronic scale; height measured (baseline only); a venous blood sample (30 ml) obtained by research staff; and surveys (described in detail below) will be interviewer administered by trained staff. Women will be asked to download the Pillsy app to their smart phones and instructions on how to use the Pillsy bottle and Pillsy app will be

given. If there is extra blood available from the venous blood sample and the patient consents, it may be used for future research to learn more about how to prevent, detect, or treat other health problems in pregnancy.

Surveys: Women will be asked to complete the following surveys at baseline:

1. Maternal Health History Questionnaire. This questionnaire was developed by the research team, and asks about maternal health history, maternal obstetric history, current and past medications, personal history, and demographics.
2. Food Frequency Questionnaire (FFQ). This questionnaire is a 125-item dietary assessment tool used to determine habitual food consumption over the past year.
3. 24-hour diet recall. The 24-hour diet recall will be collected using Nutrition Data System for Research (NDSR) software, a computer-based software application developed at the University of Minnesota that facilitates the collection of dietary recalls in a standardized fashion. Dietary intake data gathered by interview is governed by a multiple-pass interview approach. Dietary supplement use will be assessed in conjunction with collection of 24-hour dietary recalls using the Dietary Supplement Assessment Module included in NDSR. Use of all types of dietary supplements and non-prescription antacids are queried in the module. The RAs are NDSR certified through the University of Illinois Cancer Center Diet and Behavior Shared Resource.
4. GI symptoms checklist. This short survey probes for recent GI problems including abdominal pain, nausea, constipation, and diarrhea.

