**VII. Compensation.** Women will receive \$70 at baseline, \$50 at 24-28 and 34-36 weeks and \$29 and gifts of 1 pack each of diapers and wipes at labor and delivery for completing each data collection visit.

Participant incentives for pill pick-ups: Subjects will require supplementation refills 4 times outside of the research visits during the study. Participants will receive 1 pack each of diapers and wipes for each pill pick up. Women completing all aspects of the study will receive up to \$199 dollars.

**VIII. Blood processing and analyses.** All maternal blood samples will be processed at the CON research space and the cord blood samples processed at [name] 3060/3028 COMRB lab space. All samples will be stored at -80°C until analysis. The following assays will be conducted:

1) *Hemoglobin and hematocrit* will be assessed from whole maternal and cord blood in house or at Quest Diagnostics (Chicago, IL).

2) *Serum iron, transferrin saturation, and ferritin* will be quantified from maternal and cord serum at Quest Diagnostics (Chicago, IL).

3) *Soluble transferrin receptor (sTfR)* will be measured from maternal and cord serum via ELISA (R & D systems, Minneapolis, MN).

4) *Hepcidin* will be measured from maternal and cord serum via competitive ELISA at Intrinsic LifeSciences (La Jolla, CA).

5) *Erythropoietin*. Erythropoietin will be measured from maternal and cord serum via ELISA (R & D systems, Minneapolis, MN).

6) *high sensitivity C-Reactive Protein (hs-CRP)* will be measured from maternal and cord serum at Quest Diagnostics (Chicago, IL).

7) *IL-6* will be measured from maternal and cord serum via ELISA (R & D systems, Minneapolis, MN).

8) Circulating stress-related metabolite, serum 17-hydroxycorticosterone will be measured by UIC RRC metabolomics core.

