**IX. Rectal swabs processing and analyses.** All maternal rectal swabs will be processed at [name] 3060/3028 COMRB lab space and stored at  $-80^{\circ}\text{C}$  until analysis. Bacterial DNA will be extracted from the rectal swab using a commercial kit following standard procedures. The microbial community will be assessed via 16s rRNA analysis, whole genome shotgun sequencing, and qPCR.

**X. Placenta analysis.** Placenta will be used to assess gene expression of iron regulatory, inflammatory proteins, and tissue iron content. Placenta will be weighed, measured, and systematically biopsied and frozen at  $-80\text{C}$  for gene and protein analysis.

*i. Nucleic acid extraction: total RNA will be extracted from homogenized placental samples by the UIC DNA services lab and shipped to UCLA for the gene expression analyses.*

*ii. Gene (mRNA) expression: 8 representative biopsy samples will be taken, with the fetal and maternal membranes removed for later mRNA expression analyses (qPCR). The samples will be placed in RNA later and stored at  $-80\text{C}$  until analyses.*

**XI. Hair analysis.** Exposure to chronic stress will be assessed by measuring cortisol from a small hair sample (70-100 strands) using a commercial ELISA kit (Alpco Diagnostics, Salem, NH). Hair cortisol has been validated against 24-hour urine cortisol as a relevant biomarker of long-term cortisol exposure.

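### Blood draws have no set, recorded or modelled time of day, which costs precision for serum 17-hydroxycorticosterone, serum iron, transferrin saturation and hepcidin

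*Combined protocol and SAP*

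**What the plan says.** **Markers.** Exploratory Aim 1 covers "maternal stress response (i.e., serum 17-hydroxycorticosterone and hair cortisol via immunoassay", together with surveys. Specific Aim 1 describes maternal iron status and its regulators by a panel: "hemoglobin, hematocrit, ferritin, transferrin receptor, transferrin saturation, serum iron, erythropoietin, systemic inflammation and hepcidin". Section VIII, item 8, adds: "Circulating stress-related metabolite, serum 17-hydroxycorticosterone will be measured by UIC RRC metabolomics core".

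**Conditions of the draw.** The inclusion criteria (III.a) ask women to "fast for at least 2 hours prior to research data collection visits (3 occasions". The reminders for the baseline and follow-up visits (VI.a, VI.b) repeat this; women are "asked to not eat for at least 2 hours before the appointment". No hour or window is given. At delivery (VI.e) the research tubes are added to a clinical draw: "Following admission, as part of routine care, women will undergo a venous blood collection by labor and delivery staff". No fast or hour is stated there. The COVID-19 changes of 3.17.2020 attach the 24-28 week and third-trimester samples to clinically indicated draws, again without a fast or an hour. The one time-of-day instruction concerns the pills, which both arms take with dinner (V.a, V.b).

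**Analysis.** Section XIII states: "Maternal stress response, maternal iron-related parameters, and inflammation at baseline, 24-28 weeks, 34-36 weeks and labor and delivery, will be evaluated using repeated measures ANOVA". Adjustment for baseline differences is by ANCOVA. The section also plans correlations among the continuous variables at each time-point, and mediation models. Draw time appears in none of these.

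**Hair.** Section XI states: "Exposure to chronic stress will be assessed by measuring cortisol from a small hair sample". Hair is optional and is taken at baseline and 34-36 weeks only.

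**The concern.** Serum cortisol, serum iron, transferrin saturation and hepcidin change over the day. That is general physiology; the documents neither state it nor quantify it. If one woman is drawn at nine and another at four, part of the difference between them is the clock. If the same woman is drawn at different hours on different visits, part of her apparent change is the clock.

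Three consequences follow. The arm comparison for these markers has a larger residual variance, in a 40-woman trial that gives no power calculation and so has no documented margin. Within-woman change carries clock noise from both draws. The correlations and mediation models are exposed in a further way: draw time can move several markers together and so create or distort associations, and randomization does not protect an association between two post-baseline markers.

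At 24-28 weeks and at delivery no hair is collected, so the serum value is the only stress biomarker at those two of the four planned time-points.

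**Working it through.** **Documentary check.** The sections on eligibility, research visits, labor and delivery, blood processing, the COVID-19 changes and statistical analysis contain no clock time or window for a draw, no instruction to record draw time, and no time-of-draw covariate.

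**No plan figure to reproduce.** The documents give no power, effect size or SD, and no variance for any marker.

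**Illustration.** From the documents: N = 40, two-sided 0.05, and a 15% withdrawal limit. Assumed: 1:1 allocation (20 per arm); draws spread evenly over 8 hours; a log-linear fall of 1.5-, 2- or 3-fold across that span; and a log SD at a fixed hour of s = 0.3 or 0.4.

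- Clock SD: c = ln(fold)/√12
- Variance inflation: V = 1 + c²/s²
- Clock share of variance: 1 − 1/V
- Equivalent sample size: 40/V

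| Fall | c | V (s = 0.3 / 0.4) | Clock share | Equivalent n |
|---|---|---|---|---|
| 1.5-fold | 0.117 | 1.15 / 1.09 | 13% / 8% | 34.7 / 36.8 |
| 2-fold | 0.200 | 1.44 / 1.25 | 31% / 20% | 27.7 / 32.0 |
| 3-fold | 0.317 | 2.12 / 1.63 | 53% / 39% | 18.9 / 24.6 |

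**Detectable effect.** With a two-sample t test, 80% power and 20 per arm, the detectable difference is 0.91 SD without clock variation. If the clock makes up a share f of total variance, this is multiplied by 1/√(1−f). In the same SD units it becomes 0.96 at f = 10%, 1.02 at 20%, 1.09 at 30% and 1.29 at 50%. With 15% withdrawal (20 × 0.85 = 17 per arm) the series from f = 0 is 0.99, 1.05, 1.11, 1.18 and 1.40. The sample size needed to compensate rises by the factor 1/(1−f): 11% more at f = 10%, and 100% more at 50%.

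**Chance imbalance between arms.** The standard error of the arm difference in mean draw time is (8/√12) × √(2/20) = 0.73 h. At a 2-fold fall the slope is ln 2/8 = 0.0866 per hour, so this is 0.73 × 0.0866 = 0.063 log units. The clock's contribution to the standard error of the arm difference is 0.200 × √(2/20) = 0.063. The two are the same quantity, so a chance imbalance is already inside the variance inflation and must not be added to it.

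**Within-woman change.** Suppose a woman's draw hours are unrelated between visits and her clock-free values have correlation ρ. The clock share of the variance of change is then c²/(c² + s²(1−ρ)). For any ρ above zero this exceeds the single-sample share. The documents give no ρ, so no figure is offered.

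**The case against.** The strongest reply is that this is a pilot, that serum 17-hydroxycorticosterone belongs to an exploratory aim, and that the plan already assigns chronic stress to hair cortisol and collects stress surveys at 24-28 weeks. That stands, and it limits the weight of the point. It does not help serum iron, transferrin saturation and hepcidin, which are named under Specific Aim 1.

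Taking pills with dinner partly standardizes time since the last iron tablet: for an adherent woman seen in the daytime, it was the evening before. This too stands, but the interval still varies with the hour of the visit.

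The magnitude rests on assumptions and runs from trivial to severe. It also describes a single sample, whereas repeated measures with baseline adjustment are planned. The table is therefore an order of size, not an estimate for the planned model.

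Three stronger readings are tempting, and the documents support none of them:

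- *An untimed sample mostly reflects when the woman was seen.* Even under the assumptions above, the clock exceeds half the variance in only one of six scenarios (3-fold fall, s = 0.3).
- *Iron status as a whole is poorly measured.* Iron status is a panel that includes hemoglobin, ferritin and transferrin receptor, and nothing here shows a clock effect on those.
- *A chance gap in draw time biases the arm comparison in a known direction.* Such a gap is random and is already in the standard error. Nothing in the documents suggests that draw times differ systematically by arm.

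**Conclusion.** The omission is confirmed: draw time is neither fixed, recorded nor modelled, and for delivery and COVID-period draws no fast is stated either. In the randomized comparison the harm is chiefly lost precision for serum 17-hydroxycorticosterone, serum iron, transferrin saturation and hepcidin. Under the assumed spread, fall and SD, the clock is about 8% to 53% of single-sample variance, so 40 women carry the information of about 37 down to 19. At a 2-fold fall the figure is 28 to 32.

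These sizes depend wholly on the assumptions. The daily rhythms and the identity of 17-hydroxycorticosterone with cortisol are general knowledge, not statements in the documents. Associations between markers and within-woman changes need the correction as much as the arm contrast does. This is a specific and inexpensive improvement that should be made; it does not undermine the trial.

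**What to change.** 1. At every draw, including delivery and COVID-period draws, record clock time, time of last meal and time of last iron tablet.
2. Prespecify draw time as a covariate for 17-hydroxycorticosterone, serum iron, transferrin saturation and hepcidin, in the arm comparisons and in the correlation and mediation analyses. Draw time differs by visit, so the repeated-measures model must accept a time-varying covariate, for example a mixed model with one record per visit. Linear clock time is adequate for daytime visits.
3. Delivery draws can fall at any hour. Add a sensitivity analysis that leaves out the delivery draw or gives it a cyclic time term.
4. Where the study books the visit, schedule the 24-28 and 34-36 week draws near the hour of the woman's baseline draw. This cannot be required of delivery draws or of COVID-period draws tied to clinical care, so recording the time matters most there.
5. Report the serum value as a time-adjusted secondary stress marker beside hair cortisol.

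The cost is a few form fields, one covariate and slightly less flexible booking. For samples already taken, draw time may be recoverable from collection records. Meal and tablet times probably cannot be recovered reliably, so recording should start at once.
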